specialized and primary - during transition, amplifying existing barriers to accessing crucial services as disease burden is increasing. 20,21 A retrospective study showed that patients who are transitioning received 46% fewer transfusions by age 22y compared to children and were 4.7 times less likely to receive iron chelation by age 25y. 21 At Atrium Health (formerly known as Carolinas Healthcare System), a large healthcare system in the SE US that provides care for 1300 adults and 400 children with SCD, only 8-14% of EA-SCD accessed a scheduled visit with their primary care/SCD provider in 2015 with mean acute care reliance (ACR; number of acute care visits per year/ [all acute care visits + all ambulatory care visits]) rates of 42% (Fig 2). Mean acute care visits/year rose significantly from 2.1 ± 2.9 among 16- 18y to 4.2 ± 6.8 among 19 - 21y and was highest among 21 - 25y at 5.3 ± 8.5 (p<0.01). ACR (\geq 0.33) is an indicator of inadequate access to primary and preventative care. 22 EA-SCD report having inadequate information about adult care and a poor understanding of their disease and how it becomes more complex with age. $^{14, 16}$ There are significant knowledge gaps and poor communication between pediatric and adult providers that worsen the problem created by a lack of standardized EA-SCD patient education curriculum.

Limited evidence on effective transition programming:

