6.4 Schedule of Assessments

6.4.1 Screening

Subjects who consent for participation and meet the eligibility criteria for enrollment into this study will undergo the following screening assessments (See Section 3.2 for additional details on assessments):

- Collection of baseline demographic and disease characteristics:
 - o Date of birth
 - o Age
 - o Race
 - o Ethnicity
 - Gender
 - o Sickle cell genotype
 - o Zip code of residence (for urban vs rural residency status)
 - o Presence of a sibling, parent, or child (first degree relative) with SCD
 - Academic achievement
 - Disability status
 - o Marital status
 - o Employment status
 - o Living arrangement
 - Household income
- Mentor matching (Peer Mentoring sites only)
 - o Mentee day/time availability information capture
 - o Match facilitated through the Mentor1to1TM platform

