10.2 Sample Size and Accrual

Sample size calculations are based on the primary endpoint of acute care utilization visits per year (at the EA-SCD participant level). Utilizing a randomized cluster design, seven clinical sites will be randomized per arm. The sample size calculation strategy is to calculate the required minimum sample size based on an individual patient randomized design, and then inflate the sample size based on cluster randomized considerations.⁵⁴ A conservative estimate of the average acute care utilization rate for EA-SCD is 6 acute care visits per year based on data for North Carolina reported by the RuSH population surveillance project.⁴ In South Carolina, the acute care utilization rates among 18-30 y with SCD was reported as 7.17 (95% CI 6.34-7.99).55 At Atrium Health (formerly known as Carolinas Healthcare System), 295 EA-SCD had 1972 emergency department visits and 221 hospital admissions in 2015 with an average acute care

utilization rate of 6.82 visits per year. This study is designed to detect a 20% reduction in the number of acute care encounters per year (assuming a base case of 6 encounters). A 20% reduction in acute care utilization is considered clinically significant based on patient partners reporting that 1 less acute care visit a year is meaningful. Based on a two- sided alpha = 0.05significance level, 67 EA-SCD participants per arm would provide approximately 85% power to detect a 20% reduction in the number of acute care utilizations under individual randomization, assuming the number of encounters follows a Poisson distribution for rare events. The sample size will be inflated based on two parameters: the cluster size coefficient of variation and the intra-class correlation (ICC).⁵⁴ The cluster size coefficient of variation observed among the 14 participating clinical sites is 55%. Therefore, the coefficient of variation is assumed to be 60% and the ICC is assumed to be 0.05.⁵⁶ Based on these parameters, a minimum of 183 EA-SCD participants per arm (366 total EA-SCD participants) will retain approximately 85% power. To account for potential missing data and allow for robust evaluation of secondary endpoints the sample size will be increased to a total of 537 EA-SCD participants. It is estimated that this enrollment can be accomplished with an enrollment rate of 35% of the EA-SCD patient population.

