10.5.4 Primary Analysis

To evaluate the impact of PM, the acute care utilization rate per year will be compared between the PM+STE and STE arms. This will be accomplished using generalized linear mixed model with a Poisson distribution-log link construct. The model will include fixed effects for baseline acute care visits per year, the stratification factor (large sites vs small sites) and treatment arm, and a random effect for clinical site. Corresponding 95% confidence intervals will be calculated for the estimated ACU rate in each treatment arm.

Supportive and sensitivity analyses will be conducted to include potential confounding factors such as urban versus rural sites, education level, older first degree relative with SCD, genotype, age at transfer to adult care, and type of receiving provider (primary versus specialty). Univariate models will be fit for each factor, and those identified to be individually prognostic will be included in a multivariable model, and backward elimination followed by forward selection will be used to identify factors that are independently prognostic and to establish a final base model. Finally, treatment arm will be added to the base model to evaluate the impact of the intervention adjusting for significant baseline factors.

Two analyses will be conducted to estimate the impact of differential accrual between arms over time: (1) An additional term of year of enrollment will be added to the GLMM as a categorical variable; (2) We will subset the analyses to EA-SCD who were contemporaneously enrolled. Comparison of the PM+STE and STE ACU estimates from this subset to those results including all enrolled with and without controlling for year of enrollment will provide a comprehensive assessment of the potential bias due to differential accrual between arms over time. ACU rate in the STE only arm will be compared to historical ACU rates which were used for the original power calculations. Although these are comparisons to historical controls, this will provide preliminary evidence using a robust sample size of the potential impact of the structure transition education.

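### The primary model omits age at enrolment, a prognostic factor the trial already collects; prespecifying it would guard at almost no cost against an age difference between arms whose size and direction the documents do not show

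*Combined protocol and SAP*

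**What the plan says.** Section 10.5.4 specifies a Poisson mixed model with a log link and a random effect for clinical site. Its fixed part is given as: "The model will include fixed effects for baseline acute care visits per year, the stratification factor (large sites vs small sites) and treatment arm". There is no age term. Randomisation (section 4.2) is stratified on site size only, precedes study activation and is open; in section 10.2, "seven clinical sites will be randomized per arm".

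Age enters elsewhere. The supportive analyses in 10.5.4 name age at transfer to adult care, and genotype, among the potential confounders. These are screened one at a time and then pass through backward elimination and forward selection before arm is added. Section 10.5.7 carries the same participant-level factors into the heterogeneity analysis.

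The prognostic evidence is in section 1.1: "Mean acute care visits/year rose significantly from 2.1 ± 2.9 among 16- 18y to 4.2 ± 6.8 among 19 - 21y", and 5.3 ± 8.5 at 21 to 25 years (p<0.01). Section 6.4.1 provides for "Collection of baseline demographic and disease characteristics", which includes date of birth and age, so age at enrolment can be derived for everyone.

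**The concern.** By the protocol's own background data, age is associated with the outcome. The primary model can pick it up only through the visit count of the 12 months before enrolment. That count is a noisy measure of a participant's underlying rate, so adjusting for it removes only part of an age difference.

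Enrolment also differs by arm in ways that could depend on age:

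- Participants are recruited after their site's allocation is known.
- Only at mentoring sites must a participant be matched before the baseline survey (6.3, footnote b), and the survey date defines enrolment (10.1.2). Only enrolled participants are analysed (10.4).
- Matching requires at least five years between mentor and mentee (5.2.3), and mentors may be 26 (3.3). A 26-year-old mentor can take mentees only up to 26 - 5 = 21 years. If this limits matching, the mentoring arm becomes younger.
- Mentoring-site participants reconsented after a matching delay must still be eligible (3.2.1, criterion 8). Waiting makes those who stay older, while some pass the age limit and leave.

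These routes pull in different directions. A younger mentoring arm would flatter mentoring and an older one would mask a benefit. The differential-accrual analyses in 10.5.4 use year of enrolment and contemporaneous subsets, neither of which adjusts for age.

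**Working it through.** **The plan's own target.** Section 10.2 compares 6.0 with 4.8 visits per year at two-sided 0.05 and 85% power. n = (1.960 + 1.036)² × (6 + 4.8) / 1.2² = 67.3, against the stated 67. With 7 sites per arm, ICC 0.05 and cluster-size CV 0.60, the size per site is m = 67 × 0.95 / (7 - 67 × 0.05 × 1.36) = 26.04, and 7 × 26.04 = 182.3, against the stated 183. Both reproduce. The yardstick is therefore ln 0.8 = -0.223. Adding age changes neither figure.

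**Age gradient (section 1.1).** 5.3 / 2.1 = 2.52, ln 2.52 = 0.926.

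- Between assumed band midpoints of 17 and 23: 0.926 / 6 = 0.154 per year (16.7% per year).
- Spread over 16 to 25: 0.926 / 9 = 0.103 per year (10.8% per year).

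**No baseline adjustment.** A one-year difference in mean age gives a rate ratio of exp(0.103) = 1.11 to exp(0.154) = 1.17. Imitating the whole design effect would take 0.223 / 0.154 = 1.4 to 0.223 / 0.103 = 2.2 years.

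**With baseline visits in the model.** Simulations with no true effect gave these shifts in the log rate ratio per one-year arm difference in mean age. Log slopes run from 0.103 (0.108 in some runs) to 0.154. Apart from the age slope, the inputs are mostly assumptions.

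| Assumptions | Baseline visits only | Age added |
|---|---|---|
| Age SD 1.3 y, log-normal heterogeneity SD 0.7 or 1.1, log baseline count | 0.02 to 0.07 | -0.003 to 0.010 |
| Same, SD 0.7, raw count | 0.04 to 0.08 | -0.011 to 0.005 |
| Log-normal heterogeneity, 70% persistent, raw count | 0.055 to 0.093 | within ±0.01 |
| Same, log count | 0.043 to 0.078 | within ±0.01 |
| Gamma heterogeneity (shape 0.7), 70% persistent, slope 0.154 | 0.07 to 0.11 | near zero |
| Gamma (shape 0.7), other year-to-year noise, slope 0.154 | mostly 0.04 to 0.06 | not recorded |
| Same, slope 0.108 | 0.02 to 0.05 | not recorded |

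The raw-count model at heterogeneity SD 1.1 is left out because it was unstable: rate ratios of 1.09 to 1.18, and still 1.01 to 1.08 with age added, so the shift cannot be put down to age alone. None of these fits included the planned random site effect.

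The overall range of 0.02 to 0.11 is 0.02 / 0.223 = 9% to 0.11 / 0.223 = 49% of the target. With no true effect, a mentoring arm one year younger would show a rate ratio between exp(-0.11) = 0.90 and exp(-0.02) = 0.98.

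**How large a chance difference could be.** Take a within-site age SD of 2 years, 537 / 14 = 38.4 participants per site, and a between-site SD of mean age s (all but the 537 and 14 assumed). Then SE = √[(2/7)(s² + 4/38.4)]. For s = 0.25, 0.5 and 1.0, the 95% range of the arm difference is ±0.43, ±0.62 and ±1.10 years.

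**The case against.** The plan does not ignore age. Transfer is to be planned 6 to 12 months after consent, so age at transfer is roughly age at consent plus half a year to a year, and it is a named candidate alongside genotype. This stands in part. Age at transfer is, however, observed after allocation, is undefined for anyone who never transfers, is kept only if it survives selection, and enters models that are complete-case (10.5.6). None of those models alters the primary estimate.

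The slope is borrowed. It is cross-sectional, from one health system, with SDs larger than the means. It may partly reflect the move from paediatric to adult care, whereas every participant here is in paediatric care at consent. The transfer criterion may also narrow the enrolled ages. All of this stands, and the slopes above are therefore assumptions.

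A reader might infer that with seven sites per arm an age difference is likely and would be mistaken for a mentoring effect. The documents do not support that. Sites are randomised; chance age differences between them go mainly into the random site effect and widen the interval. Bias needs recruitment that depends on both arm and age. The protocol contains a route to this but gives no enrolled or mentor age distribution showing that it operates.

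Finally, adjusting for the baseline outcome and the stratifier is a defensible primary model, and in the stable runs with log-normal heterogeneity SD 0.7 or 1.1 the baseline count removed roughly half or more of the age effect. That is fair: this is an improvement, not the correction of an error.

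**Conclusion.** The point holds as a worthwhile, inexpensive strengthening of section 10.5.4. The primary model leaves out a baseline factor that the trial collects and that its own background section links to the outcome, and the supportive analyses do not fill the gap.

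If the arms differed by one year in mean age, roughly 0.02 to 0.11 would remain on the log rate ratio after baseline-visit adjustment, against a target of -0.223, and close to zero with age in the model. This rests on the borrowed slopes, on assumed heterogeneity and persistence, and on fits without a random site effect. Whether such a difference will arise, and in whose favour, cannot be determined from the documents.

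A reader might also expect a definite gain in precision. That depends on how far mean age varies between sites, which the documents do not give, and simulated gains differed widely with the assumptions, so no figure is offered.

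**What to change.** In section 10.5.4, add age at enrolment (enrolment date minus date of birth, continuous) as a fixed effect in the primary model. Carry the same term into the models for ambulatory visits, adult-provider visits, hospitalisations and readmissions. In section 10.5.3, state that age at enrolment will be reported by arm.

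If the sponsor prefers to leave the primary model as it is, specify at least one sensitivity model equal to the primary model plus age at enrolment, fixed in advance and outside the stepwise selection.

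Date the change before the final analysis and record whether interim results by arm (10.5.9) were known at the time, so that the covariate does not look chosen after the fact. The cost is one line of wording and one participant-level degree of freedom, with no new data and no change in sample size.

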6.4.2 Baseline

Subjects who are enrolled into this study will undergo the following baseline assessments (See Section 3.3 for additional details on assessments):

- SCD Provider Clinic Visit
- Historical Healthcare Utilization Data Collection: acute care utilization history (ED/ urgent
- care visits and hospital admissions) and ambulatory visits (SCD provider and Primary Care provider) in the preceding 12 months from the date of enrollment
- TIP-RFT
- MOS-SSS
- ASCQ-Me QOC
- PedsQL-SCD Module
- Health Care Transition Feedback Survey for Youth/Young Adults

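### Section 10.5.4 states no scale for the skewed baseline visit count; as a linear term in the log-link Poisson model it gives up some precision

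*Combined protocol and SAP*

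**What the plan says.** Section 10.5.4 compares the arms with a "generalized linear mixed model with a Poisson distribution-log link construct" and a random effect for site. On the covariates it says: "The model will include fixed effects for baseline acute care visits per year, the stratification factor (large sites vs small sites) and treatment arm". Section 6.4.2 fixes the baseline window: use is recorded "in the preceding 12 months from the date of enrollment", so the baseline figure is a 12-month count.

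No section states a log or square root of that count, categories or a spline. None of the sensitivity analyses in 10.5.4 varies its form.

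Section 1.1 shows how such counts are distributed at one of the participating health systems: "Mean acute care visits/year rose significantly from 2.1 ± 2.9 among 16- 18y to 4.2 ± 6.8 among 19 - 21y", and "highest among 21 - 25y at 5.3 ± 8.5".

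The sample size in section 10.2 ("67 EA-SCD participants per arm would provide approximately 85% power to detect a 20% reduction", then inflated for clustering) makes no allowance for baseline adjustment.

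**The concern.** With a log link, a linear term means that each extra baseline visit multiplies the expected rate by the same factor. If patients differ in an underlying visit rate that partly persists, the expected follow-up rate should rise roughly in proportion to prior use, not exponentially. A few very high counts then pull the fitted slope towards zero, and the covariate does less for everyone else.

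Prior use is already collected, and with seven sites per arm precision is worth having. The form is also better fixed in advance: section 4.2 says the intervention is not blinded, and section 10.5.9 plans an analysis of the primary endpoint in year 3. An unstated form could be settled after outcome data have been seen.

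**Working it through.** **1. The plan's own figures.** Inputs from section 10.2: 6 against 4.8 visits a year, two-sided alpha 0.05, 85% power, 7 sites per arm, cluster-size CV 0.60, ICC 0.05.

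- Individual randomization: n = (1.960 + 1.036)² × (6 + 4.8) / 1.2² = 67.3 per arm, against 67 stated.
- Clustering, with m = n/7: n = 67 × [1 + ((0.60² + 1)m − 1) × 0.05]. This solves to n = 63.65 / 0.3491 = 182.3, rounded up to 183, as stated.

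Both figures reproduce, and neither formula contains a baseline covariate.

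**2. Skewness of the covariate.** Inputs from section 1.1, reading ± as an SD. Variance divided by mean:

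- 16-18 years: 2.9²/2.1 = 4.0
- 19-21 years: 6.8²/4.2 = 11.0
- 21-25 years: 8.5²/5.3 = 13.6

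The SD exceeds the mean in every band. A negative binomial matched to these figures has skewness of about 2.4 to 3.1.

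**3. Why one slope cannot serve.** Suppose the slope makes 30 visits against 3 predict a tenfold rate, which is proportional. Then 3 against 0 predicts only exp(3 × ln 10 / 27) = 1.29 times the rate. If instead 6 against 3 doubles the rate, 30 against 3 predicts 2⁹ = 512 times.

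**4. Size, by simulation.** The planned Poisson mixed model was fitted to simulated 14-site trials. The assumptions, none of them given in the documents, were gamma-distributed patient rates matched to section 1.1, a site SD of 0.2 on the log scale, and the correlation between a patient's underlying baseline and follow-up rates. The measure is the variance of the estimated log rate ratio with the untransformed count, divided by that with log(count + 1). Results from 400 trials per setting, with 95% simulation intervals where available:

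| Baseline, then follow-up | Correlation 0.6 | Correlation 0.8 |
|---|---|---|
| 2.1 ± 2.9 at both times | 1.06 (1.01-1.11) | 1.23 (1.14-1.33) |
| 2.1 ± 2.9, then 4.2 ± 6.8 | 1.09 (1.03-1.15) | 1.40 (1.29-1.53) |
| 4.2 ± 6.8 at both times | 1.20 | 1.79 |
| 5.3 ± 8.5 at both times | 1.17 | 1.72 |

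At correlations of 0.3-0.4 the ratio was 1.01-1.05 in every band. Separately coded runs agreed:

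- 300 trials per setting in the upper two bands gave 1.12-1.19 at 0.6 and 1.77-1.80 at 0.8.
- A further set gave 1.01-1.06 at 0.35, 1.07-1.17 at 0.6 and 1.27-1.70 at 0.8.

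Taken together, the ratio is about 1.0-1.06 at 0.3-0.4, 1.06-1.2 at 0.6 and 1.2-1.8 at 0.8. Square roots give the inflation of the standard error: up to 3%, then about 3-10%, then about 10-34% (√1.06 = 1.03, √1.2 = 1.10, √1.8 = 1.34).

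**5. Bias.** In the single-band runs where it was tabulated, bias in the log rate ratio was about 0.01 or less under either form.

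**6. Likelihood.** In the 300-trial set refitted with a negative binomial likelihood, the ratio was 0.93-1.0, so the advantage disappeared.

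**The case against.** **The linear form is inferred.** Section 10.5.4 names the covariate and not its scale. This stands as a limit on the wording: the plan cannot be said to have chosen a wrong scale. But an untransformed term is the natural reading, and if a transformation was intended, stating it settles the matter.

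**The loss may be small.** Participants are enrolled from pediatric programs (section 3.2.1), so the 16-18 band may be closest to many baselines, and the loss is smallest there. Follow-up spans transfer to adult care, when section 1.1 says emergency visits and admissions double, so a low correlation is plausible. This stands, and it is why the range starts near 1.0.

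**A stronger reading is tempting.** A reader might infer that a linear count wastes most of the benefit of adjustment. At correlation 0.6 it cut the variance by about 34%, against 38% for the log form, in the 2.1 ± 2.9 band; in the 4.2 ± 6.8 band the figures were about 22% and 35%. Most of the gain is therefore kept. Runs that mixed the age bands gave ratios of 1.19-2.09, but they rest on age mixes and correlations (up to 0.95) that the documents do not supply. A reader might also infer bias from heavy users, or a fall in the stated power. Steps 5 and 1 of the working rule these out.

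**Overdispersion is the larger problem.** The same SDs call the Poisson likelihood into question, and a negative binomial model would remove the gain. This stands; the point is conditional on the model as written.

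**Other forms might do as well.** This largely stands. In one setting (4.2 ± 6.8, correlation 0.8, 366 participants) the SD of the estimate was 0.197 untransformed, 0.164 with log(count + 1) and 0.171 with the square root. Fixing a sensible non-linear form matters more than which one is chosen.

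**Conclusion.** The point holds as a minor improvement. As a linear term in the planned model, the baseline count gives up some of the available precision. The direction was the same in every Poisson setting reported. The size runs from negligible at correlation 0.3-0.4 to a variance ratio of 1.2-1.8 at 0.8, given gamma patient rates and a site SD of 0.2. The upper end needs both a high correlation and one of the two more dispersed age bands. The treatment estimate is not meaningfully biased, and no design figure in section 10.2 changes. Nothing was simulated for the other utilization outcomes, so the conclusion is confined to the primary model.

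**What to change.** In section 10.5.4, while the Poisson log-link model is kept, state that baseline enters the primary model as log(x + 1), where x is the number of acute care visits in the 12 months before enrollment. State also that the model will be refitted with x untransformed as a sensitivity analysis. Do not extend this to the other utilization models without separate justification.

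The cost is one phrase in the analysis plan and one extra model fit, with no new data. If the likelihood is changed to negative binomial, little or no gain should be expected, though the chosen form should still be stated.

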6.5 Schedule of Assessments (Mentors/Advisors)

6.5.1 Screening

Subjects who consent for participation and meet the eligibility criteria for enrollment into this study as mentors or advisors will undergo the following screening assessments (See Section 3.4 for additional details on assessments):

- Date of birth
- Race
- Ethnicity
- Gender
- Sickle cell genotype
- Zip code of residence (to determine urban or rural residency status)
- Presence of a sibling, parent, or child (first degree relative) with SCD
- Academic achievement
- Disability status
- Marital status
- Employment status
- Living arrangement
- Household income
- Age at transfer to adult care
- Type of SCD adult provider (primary care versus specialty)
- Mentor matching (Peer Mentoring sites only)
- Advisor matching (Peer Mentoring sites only)

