10.5.5 Secondary Analysis

EA-SCD PRO's will be analyzed quantitatively using linear mixed models for repeated measures. The models will include fixed factors for baseline scales, the site size stratification factor, treatment arm, assessment time point, and the treatment arm by time point interaction. Random factors will include investigational site and subject within site to account for correlation in responses within individual sites and within the same subject. Model-based estimates of PRO scores will be used to estimate percentage change between the treatment arms. Additionally, PRO will be analyzed using survival analysis techniques. For each EA-SCD participant, the time from baseline to a 10% worsening (TTW) in the scale will be calculated. For EA-SCD participants not experiencing a 10% worsening, TTW will be censored at the last patient reported outcome assessment. TTW will be analyzed using Kaplan-Meier techniques and Cox proportional hazards models. The

proportional hazards models will include the same factors as described for the primary analysis. Planned sensitivity analysis will be conducted to evaluate time to worsening for worsening thresholds ranging from 10% to 30%. The repeated measures and survival analyses of the EA-SCD PRO's will also include supportive and sensitivity analyses to account for potential baseline confounders as previously described in the primary analysis. EA-SCD satisfaction with transition services will be summarized descriptively.

Intervention fidelity will be analyzed descriptively. A CONSORT-type diagram will be provided, including a summary of all mentors who consented, had a background check, passed the background check, completed practice call 1, completed Peer Mentor University online training, completed practice call 2, and were matched with at least one EA-SCD. Timelines for mentors and EA-SCDs on the PM arm will be summarized descriptively. Frequency of mentor contacts will be analyzed descriptively in terms expected contacts per protocol versus actual. This will include calls placed (mentor to EA-SCD), calls answered (EA-SCD to mentor), messages sent (mentor to EA-SCD), and messages received (EA-SCD to mentor).

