10.5.7 Exploratory Analysis

Heterogeneity of Treatment Effects: We will evaluate the consistency of the intervention across site and patient level characteristics. The heterogeneity of treatment effects (HTE) will be evaluated using potential treatment effect modifiers measured prior to randomization. Site level factors will include cluster size (large vs small) and urban vs rural sites, while subject level factors are those previously listed in the multivariable modeling description. For each factor, subgroup analysis will be conducted on each of the mutually exclusive factor levels. Evaluation of the HTE will be performed qualitatively by comparing the treatment group differences across the factor levels. More formally, each subject-level factor will be evaluated using models to include treatment arm, the baseline factor, and the treatment by factor interaction.

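### Age at transfer and type of receiving provider are analysed as baseline factors, but both are settled only at transfer, after mentoring has begun

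*Combined protocol and SAP*

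**What the plan says.** Section 10.5.4 names the factors for the supportive and sensitivity analyses of the primary endpoint. The last two are "age at transfer to adult care, and type of receiving provider (primary versus specialty". All factors go through univariate screening, then backward elimination and forward selection. Treatment arm is then added in order to "evaluate the impact of the intervention adjusting for significant baseline factors".

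Two later sections take over the same list. Under Section 10.5.5 the repeated-measures and survival analyses of the patient-reported outcomes also include "supportive and sensitivity analyses to account for potential baseline confounders as previously described in the primary analysis". Section 10.5.7 restricts the heterogeneity analysis to "potential treatment effect modifiers measured prior to randomization", then states that the "subject level factors are those previously listed in the multivariable modeling description".

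On data collection, Section 6.4.1 for the emerging-adult participants begins with "Collection of baseline demographic and disease characteristics". The items beneath it cover age, genotype, education, residence and relatives with the disease, but not the two transfer variables. They are also absent from the baseline list (6.4.2) and the end-of-study update (6.4.6). They do appear in Section 6.5.1, the screening list for mentors and advisors: "Age at transfer to adult care" and "Type of SCD adult provider (primary care versus specialty".

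**The concern.** A covariate used to adjust a treatment comparison, or to define subgroups for it, should be fixed before treatment can affect it. A participant still in pediatric care has no age at transfer and no receiving provider; at consent the transfer is only planned. For mentors and advisors, who have already transferred, the same two items are historical facts.

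The purpose of mentoring is to help participants through transition, so an effect on when or where they transfer is plausible. If there is one, adjusting for these variables can remove part of the effect being estimated or introduce bias of either sign. Splitting by them compares groups formed under the intervention. Visits already counted in the outcome could also influence the timing or place of transfer; the documents do not say whether they do.

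What is at stake is the covariate-adjusted check on the primary result, the adjusted patient-reported outcome analyses and the heterogeneity analysis.

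**Working it through.** The plan gives no figure on this point to reproduce. The sample size (183 per arm) does not involve these covariates.

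**1. Order of events.**
- Sites are randomized before study activation (Section 4.2).
- A participant consents with transfer planned 6 to 12 months ahead (3.2.1) and stays in pediatrics for 6 to 12 months (1.2).
- In the mentoring arm, the match precedes the baseline surveys (6.3, footnote b), and enrolment is the date the baseline survey is administered (10.1.2).
- Calls are scheduled from enrolment (5.2.5), and months on study also run from enrolment (10.3.1).
- Transfer comes after all of these.

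Because sites are randomized first, no subject-level factor is literally measured before randomization. That wording in 10.5.7 therefore fails for the whole subject-level list.

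**2. Mentoring received before transfer.** Section 5.2.5 sets at least 4 calls a month for 3 months, then at least 2 a month. Counting transfer from enrolment:
- month 6: 4×3 + 2×3 = 18 calls
- month 12: 4×3 + 2×9 = 30 calls

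**3. Share of follow-up before transfer.** The synopsis and Section 5 give at least 6 months in pediatrics and at least 24 in adult care; Section 1.2 caps the pediatric period at 12 months. At minimum adult follow-up:
- 6/(6+24) = 20%
- 12/(12+24) = 33%

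**4. Planned values.** Neither a planned transfer age nor a planned provider is listed for participants in 6.4.1 or 6.4.2. Reading the two factors as planned values therefore does not help.

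**5. Missing values.** Section 10.4 analyses everyone enrolled, however long they stayed. Section 10.5.6 bases multivariable models on complete cases. A participant who leaves before transfer has no value and drops out of any model that contains either variable. The multiple imputation in 10.5.6 is for missing baseline data and cannot properly supply a transfer that never happened. Loss before transfer is not given; under assumed rates, out of 537:
- 5%: 537×0.05 ≈ 27
- 10%: 537×0.10 ≈ 54
- 20%: 537×0.20 ≈ 107

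**6. Illustration of the bias, on assumed figures only.** Take a true total rate ratio of 0.80, a specialty-provider share of p = 0.50 without mentoring, a rise of d with mentoring, and a rate ratio g for specialty versus primary care. The part acting through provider type is [(p+d)g + 1−p−d] / [pg + 1−p], and the adjusted rate ratio is 0.80 divided by it.
- d = 0, any g: 0.80, no change
- d = 0.10, g = 0.8: 0.88/0.90 = 0.978; adjusted 0.82
- d = 0.20, g = 0.5: 0.65/0.75 = 0.867; adjusted 0.92

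This shows only how part of the effect can be adjusted away. It does not estimate the bias in this trial.

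**The case against.** The strongest reply is that little can move.

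- **Provider type.** Each cluster has its own adult clinic (synopsis; 5.1.1), and eligibility requires planned transfer to an adult sickle cell program (3.2.1). Provider type may be largely a site feature with little variation, and then it is unlikely to pass the univariate screen.
- **Age at transfer.** On protocol, this is age at enrolment plus 0.5 to 1.0 year, so mentoring can move it by about six months at most. If both components are assumed uniform, the window's variance is 0.5²/12 = 0.021. That compares with 9²/12 = 6.75 for ages 16 to 25, about 0.3%, or with 3²/12 = 0.75 for an assumed three-year range, about 3%.
- **Figures.** The call counts and follow-up shares do not measure bias. If follow-up runs to month 60, the end of the calendar in Section 6.3, the share is 6/60 to 12/60, or 10% to 20%. Section 3.2.1 counts from consent and mentoring-arm enrolment waits for a match, so 18 calls is not a firm minimum.
- **Existing safeguards.** Section 10.5.6 compares the full and complete-case datasets, and 10.5.2 reports how many initiate transition.
- **Weight.** The synopsis says the mentoring comparator cannot be assessed quantitatively as first planned.
- **Alternative remedy.** The models could be kept and labelled as post-enrolment and exploratory.

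The points on size stand, and they keep this below the level of a primary-analysis problem. They do not make the specification valid. The close tie between the two ages favours age at enrolment, which keeps nearly all the information without the timing fault. The dataset comparisons may reveal selective loss but do not undo conditioning on a later variable. In 10.5.7 each factor gets its own interaction model, so no selection step screens it out. Relabelling would cure the description but leave the adjusted estimates open to the same bias.

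**Conclusion.** The concern holds. Sections 10.5.4, 10.5.5 and 10.5.7 describe two variables as baseline or pre-randomization when they arise 6 to 12 months after entry, with mentoring under way and part of the outcome already counted. Neither is on the participants' assessment lists.

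The size of any bias is unknown. It is zero in the adjusted models if mentoring shifts neither variable or if selection keeps neither. The visit rates by age in Section 1.1 refer to attained age, not age at transfer, so they cannot size it. The call counts assume the minimum schedule counted from enrolment, the follow-up shares assume minimum adult follow-up, and the exclusion counts assume loss rates that the documents do not give. The primary mixed model adjusts only for baseline visits and site size and is not affected. The change should be made, but the main result does not depend on it.

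**What to change.** 1. Remove both variables from the adjustment list in 10.5.4, from its reuse in 10.5.5 and from the subject-level modifiers in 10.5.7.
2. Put age at enrolment in their place, computed from date of birth (6.4.1) and enrolment date (10.1.2). It matches the start of follow-up and the 12-month baseline visit window (6.4.2). It also picks up any age difference that arises when mentor matching delays enrolment in the mentoring arm.
3. In 10.5.7, require subject-level factors to be measured at or before enrolment instead of before randomization.
4. Report transfer timing and receiving-provider type by arm, descriptively. The visits already collected (sickle cell, primary care and adult providers; 6.4.3 and 10.3.2) can supply this.

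The cost is a change of wording in the analysis plan. Date of birth and enrolment date are already collected, so no new field is needed, and the sample size does not change. The one small loss is that the supportive models no longer account for actual receiving-provider type.
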